6.1.2 Registration Process

To register a patient, the following documents should be completed (and redacted from any PMI if being completed by a site outside of SKCCC) by the Research Nurse or Study Coordinator and emailed to [contact], the lead RAVENS Study Coordinator:

- Signed Patient Informed Consent Form
- Eligibility Screening Checklist
- Copies of the following documents:
 - Diagnostic pathology and surgical reports
 - Baseline CT, Bone, MRI, and/or PET/CT scan report (scans that are applicable for enrollment)
 - Laboratory Reports:
 - Complete blood count (CBC) with differential (including absolute lymphocyte count) and direct platelet count
 - Chemistry (CMP): Albumin, SGOT (AST), SGPT (ALT), Bilirubin (total) (Direct only if clinically indicated), Calcium, Creatinine, Glucose, Total protein, Urea nitrogen, (Uric Acid only if clinically indicated), Electrolytes (including sodium, potassium, chloride and bicarbonate).
 - PSA
 - LDH
 - TESTOSTERONE
 - Treating physician's medical note mentioning/indicating all inclusion/exclusion criteria, Full Physical Examination, ECOG (performance status), Past Medical/Surgical History
 - Other documents, if requested.

Study treatment cannot begin until the patient is registered.

The Research Nurse or Study Coordinator at the participating site will then e-mail the lead RAVENS Study Coordinator at [contact] at the Coordinating Center to verify eligibility. To complete the registration process, the Coordinating Center will:

- Assign a patient study number
- Register the patient on the treatment portion/randomization of the study with the Sidney Kimmel Comprehensive Cancer Center's Clinical Research Office

- Email the patient study number to the participating site

6.2 Randomization

Eligibility work-up will include a complete blood count, serum chemistries, PSA, and radiographic studies (of involved sites) and bone scan (unless PET indicated). Once a signed informed consent has been obtained and after confirming patient eligibility, the lead data coordinator will assign a unique Study ID Number.

Treatment must not commence until the patient has received his identification number.

Stratification:

Subjects who meet eligibility criteria and qualify for enrollment will be stratified according to the following:

- 1) Institution
- 2) Initial treatment with surgery vs. radiation therapy
- 2) Prior hormonal therapy vs. no prior hormonal therapy
- 3) PSADT <6 months vs. 6-14.9 months

Process for Randomization:

The research team will utilize an interactive web response system (IWRS) to obtain the patient's randomization assignment. The lead coordinator will enter demographic and baseline characteristics in IWRS. The lead coordinator will obtain the patient's randomization assignment from the IWRS and appropriately notify the study site. Randomization will be 1:1 for SABR: SABR + Radium-223 arms and be stratified as above. Minimization approach will be applied to ensure balanced assignment to each treatment arm. The **ON STUDY date for protocol entry** will be the day that the study subject is randomized. Within 30 days from the date of randomization, is considered DAY 1 of SABR and/or SABR + Radium-223 Arm.

All institutions should allow 48 hours for patients to be randomized from the time they provide all eligibility documentation.

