6.8 Duration of Therapy

Within three weeks of the initial treatment planning imaging study, SABR will be administered in a 1-5 fractions to each treated site (within 60 days from randomization) of the study and coincides with delivery of fraction 1.

Within four weeks of randomization to the SABR + Radium-223 arm, men will receive their 1st of 6 monthly infusions of radium-223.

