B.	Serum Chemistry (CMP) includes Sodium, Potassium, Chloride, Carbon Dioxide (bicarbonate), Urea Nitrogen, Serum Creatinine, Est GFR Afr-Am(MDRD Eqn), Est GFR NonAfrAm(MDRD Eqn), Glucose, Calcium, Total Protein, Albumin, Total Bilirubin, Alkaline Phosphatase, Aspartate Amino Trans (AST), Alanine Amino Trans (ALT), Anion Gap, BUN/Creatinine Ratio, and AST/ALT ratio.
C.	CBC w/ Diff, LDH, Serum Chemistry, and Testosterone labs must be obtained within 6 months prior to enrollment.
D.	PSA lab must be obtained within 1 month prior to enrollment.
E.	Pre-study Bone Scan and CT/MRI need to be obtained within 3 months prior to enrollment. PET-CT scan is an alternative for study entry imaging to CT/MRI and/or Bone Scan
F.	Medical history review, concomitant medication review, physical exam, performance status assessment, adverse event evaluation, and the brief pain inventory assessment should be performed once , during either Day 1 or sometime during a SBRT visit (e.g. OTV).
G.	Invitae test should be performed at any time during the study or after follow up for all enrolled patients.
H.	Correlative study blood specimens should be drawn after standard of care labs, from the same line, to prevent epithelial cells from contaminating blood specimens.
I.	CT/MRI or Axumin/Choline/DCFPyL PETs should be used to measure tumor dimensions at baseline and to measure tumor dimensions and evaluate radiographic response on day 181 and on day 361. Imaging used at baseline can be further used at Day 180 and Day 360, respectively.
J.	Instructions for CAPP-Seq Sample Collection & Processing can be found in Appendix III of the protocol.
K.	Instructions for EPIC-HD CTC Sample Collection & Processing can be found in Appendix IV of the protocol.
L.	Instructions for ImmunoSeq Sample Collection & Processing can be found in Appendix V of the protocol.
M.	Instructions for Immunophenotyping Sample Collection & Processing can be found in Appendix VIII of the protocol. Only applicable for JHU/JHSOM. Not applicable for outside sites.
N.	Instructions for Invitae Saliva Kit Sample Collection can be found in Appendix VII of the protocol.
O.	Instructions for Rectal Swab Collection for Microbiome Analysis can be found in Appendix VI of the protocol.
P.	Instructions for SBRT/SABR treatment planning can be found in section 6.3 of the protocol.

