9. MEASUREMENT OF EFFECT

9.1 Antitumor Effect – Metastatic Tumors

For the purposes of this study, patients should be re-evaluated for radiographic response 6- and 12-months after randomization. Trial radiologists evaluating for treatment responses will be blinded to the treatment group and treatment specifics (lesions treated with SABR).

Response and progression will be evaluated in three ways:

- 1) Using Response Evaluation Criteria in Solid Tumors (RECIST 1.1) Committee definition. Changes in only the largest diameter (uni-dimensional measurement) of the tumor lesions are used in the RECIST criteria.
- 2) Lesions by bone scan will be evaluated as positive, negative or no change. MRI of the bone lesion can be used to clarify equivocal lesions.
- 3) Serial PSA changes.

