14.2 Sample Size/Accrual Rate/Follow-Up

The primary endpoint will be progression-free survival (PFS). Data from STOMP and ORIOLE on this patient population indicate that $\geq 50\text{-}60\%$ would show progression as defined above within a 12-month period from SABR, and a median PFS around 10 months. (72-74). We hypothesize that the addition of radium-223 will be able to reduce the risk of progression by 50%. A sample size using a 1:1 randomization scheme of 30 patients per arm will provide 80% power to detect an increase of median PFS from 10 months to 20 month (corresponding to hazard ratio 0.5) with type I error = 0.1, using one-sided log-rank test. The calculation assumes 18 months of accrual time with an additional follow-up of 12 months after the last patient is randomized. To account for 5% early drop out, we will randomize a total of 64 patients (32 per arm).

There will be no interim analysis for futility, since the progression endpoint will not have been reached by a meaningful number of patients before full accrual.

Follow-up (Every 3-6 months for 24 months or until death)

Patients will be followed for 2 years after Day One of trial or until death. Patients withdrawn from the study because of AEs will be followed until the adverse event has either resolved or stabilized. Reasons for premature withdrawal should be determined and noted.

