14.4 Analysis of Primary Objective

This is a randomized, Phase II trial of SABR *versus* SABR + Radium-223 in oligometastatic hormone sensitive prostate cancer patients. Minimization approach (77) will be applied to ensure balanced assignment to each treatment arm by stratification factors: 1) Institutional; 2)Initial treatment with surgery vs. radiation therapy; 3) Prior hormonal therapy vs. no prior hormonal therapy; and 4) PSADT <6 mos vs. 6-14.9 mos. Baseline PSA level is defined as that measured Day 1 following randomization. Progression is defined as per section 9.6.2.

The primary outcome of interest is PFS, defined as the time from the date of randomization to the date of disease progression or death, whichever happens earlier. For those who are alive and do not have progressive disease, PFS will be censored at the time of the last scan. Kaplan-Meier method will be used to summarize PFS and log-rank test will be used to compare PFS between the two arms. The analysis population includes all randomized subjects based on intent-to-treat principle.

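### The calendars count PFS visits from Day 1 while other sections count from randomization, so an arm difference in start lag could bias the log-rank test

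*Combined protocol and SAP*

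**What the plan says.** **Day 1 and treatment start.** Section 6.2 makes the randomization date the on-study date and then separates Day 1 from it: "Within 30 days from the date of randomization, is considered DAY 1 of SABR and/or SABR + Radium-223 Arm". The same window covers both arms. Calendar footnote V (SABR arm) and footnote Y (combination arm) require the Day 1 research blood to be taken before SABR or radium-223, which ties Day 1 to treatment start. Section 6.8 allows SABR "within 60 days from randomization", with no limit to one arm. For the combination arm only, it adds: "Within four weeks of randomization to the SABR + Radium-223 arm, men will receive their 1st of 6 monthly infusions of radium-223".

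**Visit times.** The calendars in Section 8 have a Day 1 column and place later visits at Day 181 and Day 361, each with a 7-day window either side. The footnotes tell sites to "evaluate radiographic response on day 181 and on day 361". Section 9.1 says "patients should be re-evaluated for radiographic response 6- and 12-months after randomization", and Section 6.7.1 times the PSA draws at months 3, 6 and 12 from randomization for all patients. Section 6.7.2 gives imaging at 6 and 12 months without naming an origin.

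**PFS clock.** Section 14.4 has PFS "defined as the time from the date of randomization to the date of disease progression or death". Section 9.5.5 starts PFS at the beginning of treatment.

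**The concern.** Much of the progression in this trial will be found at scheduled PSA and imaging visits, so the recorded event date is often the visit date. If a patient's visits are counted from a Day 1 that falls some weeks after randomization, while PFS is counted from randomization, the recorded event moves later by that lag. If the typical lag differed between arms, the arm that starts later would appear to progress later even with no treatment effect.

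The log-rank test uses only the order of the event times. With events bunched at a few visits, a small systematic shift can place most of one arm's events at a visit behind the other arm's. The trial is unblinded. Only the combination arm has a first-infusion limit, blood-count thresholds before the first infusion and drug-ordering constraints, so a difference in lag is plausible even though none is stated. At stake is the primary comparison in a 64-patient trial.

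**Working it through.** **1. The plan's own figure.** The inputs from Section 14.2 are "30 patients per arm will provide 80% power to detect an increase of median PFS from 10 months to 20 month", "with type I error = 0.1, using one-sided log-rank test", 18 months of accrual, 12 further months of follow-up and 5% drop-out.

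- Events needed (Schoenfeld): 4(1.2816 + 0.8416)² / (ln 0.5)² = 37.5, so 38.
- Event probability with uniform accrual A and follow-up F: 1 − [exp(−λF) − exp(−λ(A+F))] / (λA). With λ = ln 2/10 this is 0.751. With λ = ln 2/20 it is 0.509.
- Expected events: 30 × (0.751 + 0.509) = 37.8. Power: Φ(√37.8 × 0.693/2 − 1.2816) = 0.802.
- Drop-out: 60/0.95 = 63.2, so 64.

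The sample size reproduces and does not depend on the visit anchor.

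**2. Can a site satisfy both visit rules?** Day 181 is 180 days after Day 1, so it lies L + 180 days after randomization, where L is the lag. Six months is 6 × 30.44 = 182.6 days. The 7-day window reaches that date only if L ≤ 182.6 − 180 + 7 = 9.6 days, or 7 days if six months is read as 180 days. At L = 30 the calendar window is days 203 to 217 after randomization. The two rules conflict for most of the permitted 30 days.

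**3. What a lag does to the test.** The simulation has 32 patients per arm, exponential PFS, 18 months of accrual and 12 months of follow-up. Progression is dated at the first visit after it occurs (months 3, 6, 12, 18, 24, within 7 days), PFS runs from randomization, and the log-rank test is one-sided at 0.10. **The documents give no lag data. Every lag range below is an assumption, uniform over the days shown.**

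| Visit anchor and lag (days) | Type I error | Power at HR 0.5 |
|---|---|---|
| Randomization | 0.10 | 0.77 |
| Day 1, both arms 0–30 | 0.10–0.11 | 0.76–0.77 |
| Day 1, SABR 0–60, combination 0–28 | 0.05 | 0.66 |
| Day 1, SABR 0–20, combination 10–30 | 0.25 | 0.90–0.91 |
| Day 1, SABR 10–30, combination 0–20 | 0.03–0.04 | about 0.6 |

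Equal lags leave the test unbiased. With SABR 0–30 days and combination 0–28 days, the type I error is about 0.09, close to nominal. The last two rows have a mean difference of 20 − 10 = 10 days and stay inside the 30-day window.

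**4. Sensitivity to off-schedule detection.** If half of the events are dated exactly instead of at a visit, the type I error in the last three rows becomes about 0.08, 0.14 and 0.07.

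**5. Would moving the PFS clock to treatment start solve it?** No. With 30 per arm, SABR starting on the day of randomization, the combination arm starting 30 days later, and both visits and clock counted from treatment start, type I error is 0.05 and power 0.65. Counting from treatment start ignores the extra time at risk before a later start.

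**The case against.** The strongest reply is that the protocol already anchors these assessments correctly. Sections 6.7.1 and 9.1 name randomization, and Section 12.1 makes the Day 180 forms due within six months of randomization, which fits poorly with a Day 180 counted from a later Day 1. On that view the calendar numbering is loose labelling. This stands in part: it cannot be said that visits *are* counted from Day 1, only that the calendars number them so. But sites schedule from the calendars, and Section 6.2 expressly separates Day 1 from randomization.

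Three stronger readings are tempting, and the documents do not support them.

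- *Day 1 may fall 60 days after randomization.* The 60 days in Section 6.8 are attached to SABR delivery. The sentence is garbled and may link a study day to the first fraction, but the only stated Day 1 window is 30 days.
- *The arms have different lags.* No section says so. The Day 1 window and the 7-day visit window are common to both arms.
- *The false-positive rate is about doubled.* Rates of 0.19 to 0.21 arise if SABR alone starts within 28 days and the combination within 60. The only four-week limit belongs to the combination arm. Set the way the text sets them, the windows give the conservative case: type I error 0.05 and lost power.

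It is also fair that progression need not be found at a scheduled visit. Section 6.7.2 allows earlier imaging, and Section 9.5.5 counts symptoms, start of ADT and death. Months 18 and 24 require PSA but not imaging, and the PSA confirmation rule was not modelled. These points reduce the size of the effect, as step 4 shows, but do not remove it.

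**Conclusion.** Two conflicts are established from the text: the visit anchor (calendar Day 1 against randomization) and the PFS origin (9.5.5 against 14.4). For a lag beyond about 7 to 10 days, a site cannot meet both rules for the six-month visit.

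Bias in the log-rank test is a conditional risk. It needs sites to schedule from Day 1 and the lag to differ by arm. If both hold, a 10-day mean difference could move a nominal 0.10 to about 0.25 or 0.03–0.04, or to about 0.14 or 0.07 if half of the events are dated off schedule. The direction depends on which arm starts later. These figures rest on assumed lag distributions and exponential PFS and should be read as illustrations. A reader might infer that the test is already anti-conservative; the documents do not show that. This is a free improvement, worth making because it closes a route to arm-dependent assessment times in an unblinded trial.

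**What to change.** - In both calendars, count every PSA and imaging assessment used for PFS from the date of randomization, as Sections 6.7.1 and 9.1 already do, and name that origin in 6.7.2.
- Keep Day 1 numbering for treatment-related visits only.
- Use randomization as the single PFS origin in both 9.5.5 and 14.4, in line with the intent-to-treat analysis. Changing the PFS origin without the visit anchor would leave the problem in place.
- Reconcile the 30-day Day 1 window in 6.2 with the 60-day SABR window in 6.8, and state which event defines Day 1 in each arm. Which window applies is for the investigators to decide.

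The cost is a wording change to the calendars and two sections. It needs no extra visits, scans or patients.

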6.3 Diagnostic Procedures

A bone scan and CT (and/or MRI of questionable sites) must be available or will be obtained within 3-months of randomization for confirmation of oligometastases. And/or DCFPyL, Axumin- or Choline-PET/CT scan must be made available and obtained within 3-months of randomization. A CT- and/or MRI-simulation scan will be performed for tumor localization and radiation planning using rigid immobilization appropriate for stereotactic treatment.

6.4 Therapeutic Procedures

Upon confirmation of eligibility and enrollment in the study, the following will be confirmed or completed:

- 1) Demographics review, medical history and clinical exam
- 2) Review of concurrent medications
- 3) Vital signs, height and weight
- 4) PSA, Testosterone, CBC, Chemistry Panel, LDH, CAPP-seq, EPIC HD-CTC and ImmunoSEQ. Immunophenotyping will only occur at Coordinating Center. Research Labs are voluntary and based on site participation.
- 5) CT and/or MRI scan of the involved site(s) (if not previously conducted within 3 month of enrollment). CT/MRI/Bone Scan can be supplemented if PET-CT is completed.
- 6) Bone scan (if not previously conducted within 3 month of enrollment).
- 7) Invitae Test
- 8) ¹⁸F-DCFPyL (“PyL”) PET/CT Diagnostic Imaging Protocol. **Only for participating sites.**

The subjects accrued at the outside institutions may be scanned on a different scanner than that used at Johns Hopkins. This therapeutic procedure is only applicable for participating sites.

- There are no dietary or food restrictions for this research study.
- Fasting is not required prior to ¹⁸F-DCFPyL (PyL) dosing and PET/CT imaging. Increased fluid intake should occur before and after image acquisition to maintain proper hydration throughout the study period, decrease radiation exposure to the urinary bladder and improve image quality.
- Subjects should be encouraged to void as frequent as possible. At a minimum void post study drug injection, immediately before imaging, and after imaging.
- A single administration of ¹⁸F-DCFPyL Injection will be administered prior to PET/CT imaging
- ¹⁸F-DCFPyL Study Drug Administration:
 - Place an IV catheter in an antecubital vein or an equivalent venous access.
 - Ensure patency of the line with a saline flush.
 - Inject a bolus of the prescribed dose of 18F-DCFPyL (9 mCi or 333 MBq) of into the IV line or equivalent venous access by slow push from the appropriately shielded syringe according to normal local practices.
 - Administer an intravenous flush (e.g., 5-10 ml sterile Sodium Chloride Injection, 0.9%), to ensure full delivery of the dose.

- ^{18}F -DCFPyL PET/CT imaging will be performed using local PET/CT scanners with low dose CT for attenuation correction and anatomic localization.
- Subjects will be asked to void prior to imaging. After voiding, a whole-body CT and PET scan will be acquired starting from the mid-thigh through the skull. Whole body PET/CT scans must be obtained within 60-120 minutes following the ^{18}F -DCFPyL dosing.

The study PI, co-I's or study coordinator will contact the patient around 7 days (3 - 10 days) after the PET/CT study to inquire about delayed side effects. If there are suspected problems the patient will be asked to return for a clinic visit for a follow-up clinic visit.

9) SBRT/SABR treatment planning

CT- and/or MRI-simulation will then be performed with fabrication of a radiation therapy immobilization device (such as the Alpha Cradle) which will be custom made for each patient. The treating radiation oncologist will identify the location of the tumor. Gross tumor volume (GTV) delineation will be performed with a diagnostic radiologist on sequential axial computed tomography images. A radiosurgical treatment plan will be developed based on tumor geometry and location. The clinical tumor volume (CTV) will equal the GTV. The dose will be prescribed to the minimal isodose line that completely covers the planning target volume (PTV) PTV (=CTV plus a 3-5 mm margin). Adjacent normal structures including but not limited to the heart, esophagus, aorta, spinal cord, kidneys, rectum, bowel, liver, and stomach within 5 cm of the CTV will be identified for the purpose of limiting incidental radiation to these structures.

In addition, prior to treatment delivery, a four-dimensional cone beam CT study will be performed on individual patients to assess respiration in these patients and to determine tumor targeting accuracy for those tumors that may be subject to respiratory motion such as those in the bones of the thorax. If tumor motion is greater than 5 mm, PTV will be expanded to account for respiration.

SBRT/SABR will be delivered in 1 to 5 fractions, and the dose and fractionation schedule will depend on the size and location of the lesion and the surrounding normal tissue constraints in accordance with AAPM Task Group 101 recommendations. Typical doses include 16 – 24 Gy in 1 fraction, 48 – 50 Gy in 4 fractions, and 50 – 60 Gy in 5 fractions. For example, isolated osseous lesions will be treated in a single fraction, lesions close to the lung and liver lesions will be treated in 3 to 5 fractions depending on their size (5 fractions for ≥ 3 cm or central tumors in close proximity to the mediastinum), and bone lesions will be treated in 5 fractions if small-bowel constrains fewer doses.

Within three weeks of the initial treatment planning imaging study, SBRT/SABR will be administered using image-guidance. An Alpha Cradle (or equivalent

immobilization device) will be used to minimize movement of the chest, spine, and abdomen during treatment. During treatment, real time cone beam CT images of the patient's body site of interest will be obtained. Cone beam CT scan will be obtained immediately prior to treatment and will be repeated until the treatment shift, required to align the CT planning scan and the cone beam CT scan performed on the day of treatment cone beam CT, is within tolerance for the body site.

Patients will be evaluated for adverse events/toxicities during their treatment.

The dose limits for surrounding critical structures are as follows:

Spinal Cord: maximal allowable dose should be = 800 cGy in 1 fraction

Lung: 2/3 of the lung volume should be kept under 500 cGy.

Heart: 50 % of the heart volume should be kept under 1000 cGy.

Esophagus: 50 % of the esophagus volume should be kept under 1000 cGy and no single point dose in the esophagus should exceed 2000 cGy.

Brachial Plexus: maximal allowable point dose = 1000 cGy

Liver: One third of the uninvolved liver or approximately 700 cc <15 Gy.

Kidneys: 75% of volume of each kidney <5 Gy.

Small Bowel: <5% of bowel limited to <20 Gy.

9) Radium-223

Dosage Forms and Strength:

Radium-223 is available in single-use vials containing 6 mL of solution at a concentration of 1,000 kBq/mL (27 microcurie/mL) (1,100 kBq/mL (29.7 microcurie/mL) after implementation of the NIST update) at the reference date with a total radioactivity of 6,000kBq/vial (162 microcurie/vial) (6,600 kBq/vial (178 microcurie/vial) after implementation of the NIST update) at the reference date.

Preparation:

Radium-223 is a ready-to-use solution and should not be diluted or mixed with any solutions. Each vial is for single use only. Parenteral drug products should be inspected visually for particulate matter and discoloration prior to administration, whenever solution and container permit.

Before the first administration of Xofigo, the absolute neutrophil count (ANC) should be $\geq 1.5 \times 10^9/L$, the platelet count $\geq 100 \times 10^9/L$ and hemoglobin $\geq 10 \text{ g/dL}$. Before subsequent administrations of Xofigo, the ANC should be $\geq 1 \times 10^9/L$ and the platelet count $\geq 50 \times 10^9/L$. If ANC is not within normal limit prior to protocol window, then CBC can be drawn, per treating physician advisement. All doses 6 doses should still be administered regardless of

treatment delay due to ANC. Unless, there is no recovery to these values within 6 to 8 weeks after the last administration of Xofigo, despite receiving supportive care, then further treatment with Xofigo should be discontinued. Patients with evidence of compromised bone marrow reserve should be monitored closely and provided with supportive care measures when clinically indicated. Discontinue Xofigo in patients who experience life-threatening complications despite supportive care for bone marrow failure.

Dosage:

The dose regimen of radium-223 is 50 kBq (1.35 microcurie) (55 kBq/kg (1.49 microcurie/kg) after implementation of the NIST update) per kg body weight, given at 4 week intervals for 6 injections.

The volume to be administered to a given patient should be calculated using the:

- Patient's body weight (kg)
- Dosage level 50 kBq/kg body weight (55 kBq/kg after implementation of the NIST update) or 1.35 microcurie/kg body weight (1.49 microcurie after implementation of the NIST update)
- Radioactivity concentration of the product (1,000 kBq/mL; 27 microcurie/mL (1,100 kBq/mL after implementation of the NIST update; 29.7 microcurie/mL) at the reference date
- Decay correction factor to correct for physical decay of radium-223.

The total amount (volume to be drawn into the syringe) to be administered to a patient should be calculated as follows:

Volume to be administered (mL) =
Body weight (kg) x dose (50 kBq/kg b.w)^a/
DK factor x 1,000 kBq (0.027 mCi)/mL^b

^a 55 kBq/kg after implantation of the NIST update

^b 1,100 kBq (29.7 microcurie)/mL after implantation of the NIST update

Decay Correction Factor Table

Days from Reference Date	Decay Factor	Days from Reference Date	Decay Factor
-14	2.296	0	0.982
-13	2.161	1	0.925
-12	2.034	2	0.870
-11	1.914	3	0.819
-10	1.802	4	0.771
-9	1.696	5	0.725
-8	1.596	6	0.683
-7	1.502	7	0.643
-6	1.414	8	0.605
-5	1.330	9	0.569
-4	1.252	10	0.536
-3	1.178	11	0.504
-2	1.109	12	0.475
-1	1.044	13	0.447
		14	0.420

The Decay Correction Factor Table is corrected to 12 noon Central Standard Time (CST). To determine the decay correction factor, count the number of days before or after the reference date. The Decay Correction Factor Table includes a correction to account for the 7 hour time difference between 12 noon Central European Time (CET) at the site of manufacture and 12 noon US CST, which is 7 hours earlier than CET.

Immediately before and after administration, the net patient dose of administered radium-223 should be determined by measurement in an appropriate radioisotope dose calibrator that has been calibrated with a National Institute of Standards and Technology (NIST) traceable radium-223 standard (a new reference vial will be sent to each center corresponding to the updated NIST reference material) and corrected for decay using the date and time of calibration. The dose calibrator must be calibrated with nationally recognized standards, carried out at the time of commissioning, after any maintenance procedure that could affect the dosimetry and at intervals not to exceed one year.

Each center must perform the Radium Ra 223 dichloride dial setting on their relevant dose calibrator(s) (upon notification by Bayer each center is required to update the dial setting to correspond to the new NIST standard). The current dial settings are to remain in effect until Bayer obtains FULL approval from the FDA for implementation. In preparation for implementation of the NEW dial setting, the clinical study center will receive a sealed vial labeled NIST standard containing a Radium Ra 223 dichloride solution for calibration only. The vial is identical to the vials used for study treatment. The amount of Radium Ra 223 dichloride in the vial will be stated on the label. Instructions for the dial setting, including the calibration log form, will be enclosed with the dispatch of the calibration sample.

NIST Standardization Update:

The qualification of radium-223 radioactive in Xofigo (radium-223 dichloride; BAY 88-8223) is based on the primary standardization performed by the US NIST. National Institute of Standards and Technology prepares the standard reference material (SRM) using an official dial setting (primary standardization) as published [20]. The NIST SRM is used to calibrate the instruments in production and quality control for both the drug substance and drug product. Additionally, the NIST SRM is used to prepare the NIST traceable Ra-223 reference materials which are then sent to the end-users (e.g., nuclear medicine laboratory physicians or technicians) for dial-setting of their dose calibrators, to allow verification of the patient dose.

In 2014, NIST performed a re-assessment of the primary standardization based on preliminary information suggesting a potential discrepancy of approximately 8-10% between the published NIST primary standardization [20] and results obtained by other national metrology institutes (United Kingdom, Germany, Japan). After completion of the re-assessment, NIST reported their findings [21] and had issued a revised NIST SRM in 2015. The discrepancy in the NIST standardization was determined to be -9.5% between activity values obtained using the old reference standard relative to the new primary standardization. Consequently, the current numerical values need to be corrected by approximately +10.5%.

The current NIST standard for radium-223 dichloride will remain in effect until the FDA has fully approved the regulatory variation submitted for Xofigo and is anticipated in the 2nd quarter of 2016. All sites are expected to begin preparation for the updated NIST standardization and obtain all necessary IRB approvals. Bayer will continue to notify sites about the status of the regulatory approval and the date that the updated NIST standardization is to be implemented. Upon notification, and prior to the implementation, all sites are expected to add a new dial setting to their dose calibrators for the new NIST standardization for radium-223 dichloride, which should be documented on the appropriate study forms.

The change in the numerical description of the patient's dose, product strength and labeled vial activity does not impact the safety or efficacy of Xofigo. The change in the NIST radium-223 standard has no impact on subjects; dose subjects are receiving, and will continue to receive. Subjects will receive the same actual dose and volume that was studied in Study 15245 (BCI-06 dosimetry study) and is associated with the proven safety and efficacy of radium-223 dichloride, though the stated nominal radiation dose received is being updated to reflect the new standard. The formula for the calculation of the volume to be administered has to be changed respectively. (see dose section) Subjects who are on-treatment at the time the new NIST reference standard goes into effect should be notified of this change and

should be required to sign a Patient Information Sheet to acknowledge that they have received information on the updated NIST standard calibration. All patients randomized after the new reference standard is in effect should sign a revised Informed Consent Form that contains the updated NIST standardization.

Administration:

Radium-223 should be administered by slow IV injection over 1 minute. The IV access line or cannula should be flushed with isotonic saline before and after injection of radium-223.

Handling and Patient Protection:

Radium-223 is primarily an alpha emitter, with a 95.3% fraction of energy emitted as alphaparticles. The fraction emitted as beta-particles is 3.6%, and the fraction emitted as gammaradiation is 1.1%. The external radiation exposure associated with handling of patient doses is expected to be low, because the typical treatment activity will be below 8,000 kBq (216 microcurie). (8,800 kBq (238 microcurie) after implementation of the NIST update) In keeping with the **As Low As Reasonably Achievable (ALARA)** principle for minimization of radiation exposure, it is recommended to minimize the time spent in radiation areas, to maximize the distance to radiation sources, and to use adequate shielding. Any unused product or materials used in connection with the preparation or administration are to be treated as radioactive waste and should be disposed of in accordance with local regulations. The gamma radiation associated with the decay of radium-223 and its daughters allows for the radioactivity measurement of radium-223 and the detection of contamination with standard instruments.

General warning:

Radium-223 should be received, used and administered only by authorized persons in designated clinical settings. The receipt, storage, use, transfer and disposal of radium-223 are subject to the regulations and/or appropriate licenses of the competent official organization.

Radium-223 should be handled by the user in a manner which satisfies both radiation safety and pharmaceutical quality requirements. Appropriate aseptic precautions should be taken.

Radiation protection:

The administration of radium-223 is associated with potential risks to other persons (e.g., medical staff, caregivers and patient's household members) from radiation or contamination from spills of bodily fluids such as urine, feces, or vomit. Therefore, radiation protection precautions must be taken in accordance with national and local regulations.

For drug handling:

Follow the normal working procedures for the handling of radiopharmaceuticals and use universal precautions for handling and administration such as gloves and barrier gowns when handling blood and bodily fluids to avoid contamination. In case of contact with skin or eyes, the affected area should be flushed immediately with water. In the event of spillage of radium-223, the local radiation safety officer should be contacted immediately to initiate the necessary measurements and required procedures to decontaminate the area. A complexing agent such as 0.01 M ethylene-diaminetetraacetic acid (EDTA) solution is recommended to remove contamination.

For patient care:

Whenever possible, patients should use a toilet and the toilet should be flushed several times after each use. When handling bodily fluids, simply wearing gloves and hand washing will protect caregivers. Clothing soiled with radium-223 or patient fecal matter or urine should be washed promptly and separately from other clothing.

